Electrophysiologic examination of muscles can provide diagnostic information as to the underlying process: myopathy, neuropathy, neuronopathy or neuromuscular junction disorders. There are currently two primary types of EMG techniques or methods: intramuscular or needle EMG (NEMG) and surface EMG (SEMG). NEMG involves the insertion of a needle electrode directly into the muscle to be examined and is considered the gold standard for assessing the muscle attributes of neuromuscular diseases. NEMG allows the clinician the ability to provide a precise evaluation of key indicators of neuromuscular function such as

spontaneous activity and motor unit action potential (MUAP) recruitment and morphology. These indices are utilized to: 1) differentiate between primary muscle pathology and muscle dysfunction secondary to nerve injury 2) characterize the nature of the pathology by the assessment of denervation activity which is typically indicative of an active disease process 3) assess re-innervation changes indicating disease chronicity and 4) define the topographical distribution of the neuromuscular disorder. ¹

However, NEMG is invasive and painful. Insertion of the needle damages the pierced tissues causing swelling and bleeding and nociceptor activation causes pain. There is risk of infection, viscus perforation and disease transmission. ³ These drawbacks are especially evident in areas of the body that are sensitive or dangerous places to use a needle such as the mouth/pharynx, eyes, ears, GI tract, urinary system, and myocardium. Consequently, NEMG is not used in these areas routinely in EMG laboratories. In an awake participant, needle electrode placement into oral or pharyngeal muscles is constrained by the gag reflex, insertion pain, procedure fear, local trauma, and bleeding risk. Once inserted, the needle electrode must be optimally positioned to record muscle activity. This requires repositioning of the needle in the muscle which further challenges participant tolerance and compliance.

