Due to the drawbacks and limitations of both NEMG and SEMG, routine clinical EMG examination of these types of muscles is not feasible or practical. Therefore, there is a need to provide an EMG sensor that can overcome the drawbacks of NEMG and the deficiencies of SEMG to provide accurate diagnostic data for the clinical evaluation of participants with neuromuscular disorders affecting muscles located in body cavities or associated with internal organ systems.

For that reason, we propose a pilot study to examine the diagnostic utility of a novel transmembrane surface sensor, and compare signals obtained with the TM-EMG sensor to conventional NEMG signals participants from healthy volunteers to those with documented neurologic pharyngeal muscle dysfunction (ALS and muscular dystrophy) and to those with severe OSA.

STUDY SETTING

Study recruitment will occur at the SENTA Clinic in San Diego, CA, USA; a tertiary referral center which focuses on diseases of the head, neck, brain and spine. All EMG testing procedures will be performed in this clinic under the supervision of an expert otolaryngologist who will obtain the EMG tracings. In-Laboratory polysomnogram (PSG) studies will be performed at AmeriSleep Diagnostics in San Diego, CA, USA; a comprehensive and ACHC accredited sleep diagnostic facility.

STUDY DESIGN

This is a prospective, cohort, pilot study of adults from healthy volunteers to those with documented neurologic pharyngeal muscle dysfunction (ALS and muscular dystrophy) and to those with severe OSA; assessing diagnostic properties of EMG studies using a conventional needle and TM-EMG sensor in pharyngeal muscles.

OBJECTIVES and HYPOTHESIS

Primary Objective

To validate the TM-EMG sensor as a non-invasive technique for the assessment of neuromuscular function in the upper airway.

Secondary Objective

To elicit, using the TM-EMG sensor, neuromuscular findings that correlate to OSA in affected participants.

Study Hypothesis

The primary hypothesis is that transmembrane EMG (TM-EMG) examination of muscles located within internal body cavities and organ systems such as the oropharynx using the TM-EMG sensor will have similar diagnostic findings to the conventional NEMG examinations and that neurogenic changes will be observed in OSA.

Eligibility Criteria

Inclusion Criteria

- Gender: Male and or female
- Age: 18-70 years

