The principal investigator will then take his turn at assessing the same muscles. The palatoglossus will be examined in the same location using the same TM-EMG probe. Once an optimal EMG recording is obtained, the TM-EMG probe will be released off the mucosal surface and a very fine concentric needle electrode (Ambu Neuroline 25 mm x 30G) will be placed into the palatoglossus using the procedure as described below. Needle insertion will be done in a straight line through the mucosal membrane into the midpoint of the muscle at the desired depth. 1-3 needle insertions will be used to obtain a diagnostic-quality EMG tracing from each muscle. The needle is placed in the same location tested by the TM-EMG probe. Once both tracings are recorded, the contralateral palatoglossus will be tested via both TM-EMG and NEMG. The principal investigator will then obtain bilateral genioglossus EMG using the same protocol that was used for the palatoglossus.

The principal investigator will also obtain EMG data from both left and right palatopharyngeus using the TM-EMG probe and associated protocol. However, due to anticipated difficulty with gag reflex associated with the palatopharyngeus, NEMG will not be used at this site, and testing of this muscle will only be performed by the principal investigator. In total, 6 muscles locations will be tested via TM-EMG, and 4 muscle locations by NEMG.

The free-run EMG tracing for both TM-EMG and NEMG will be displayed on an oscilloscope and heard through an audio-amplifier. All EMG recordings will be made using standard gain and sweep speed settings. Waveforms for both TM-EMG and NEMG tests will be recorded on a Cadwell Sierra Summit EMG system.

We anticipate the recording time per muscle will be approximately 10 seconds. If participant exhibits intolerance during an individual muscle test, that particular muscle test will be discontinued.

The participant will be examined at the conclusion of the EMG procedures for excessive bleeding or swelling. The participant will have blood pressure, heart rate, and respiratory rate checked for stability immediately upon completion of testing and prior to discharge. The participant will be given written instructions on how to contact the research staff should any adverse events arise, such as a sore throat, fever, testing site irritation or any other study

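### At the four sites where both devices are used, the planned safety data cannot separate harms of the TM-EMG probe from harms of the needle, although a needle-free pass already exists where they could be recorded

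*Combined protocol and SAP*

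**What the plan says.** **Sequence.** Under EMG Testing Procedure, benzocaine is applied first. The co-investigator then records TM-EMG from both palatoglossus and both genioglossus muscles. Next, "The principal investigator will then take his turn at assessing the same muscles": the principal investigator repeats TM-EMG at each of these sites and follows it with the needle. On placement: "The needle is placed in the same location tested by the TM-EMG probe". On number: "1-3 needle insertions will be used to obtain a diagnostic-quality EMG tracing from each muscle".

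**Probe-only sites.** The principal investigator also tests both palatopharyngeus muscles with the probe. There, "NEMG will not be used at this site, and testing of this muscle will only be performed by the principal investigator". The section's own total is: "In total, 6 muscles locations will be tested via TM-EMG, and 4 muscle locations by NEMG".

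**Safety observation.** The site examination comes once, at the end: "The participant will be examined at the conclusion of the EMG procedures for excessive bleeding or swelling". Vital signs are taken before testing starts and after it ends. Staff contact the participant on days 1 and 7, and the timing rule for relatedness refers to the study intervention as a whole. A muscle test that is not tolerated is stopped, with no instruction to record which device was in use. The Adverse Event Monitoring section only points back to the Interventions section, and Statistical Methods names no analysis of adverse events or tolerability.

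**Purpose.** The background motivates the probe by the drawbacks of needle EMG: "However, NEMG is invasive and painful". The primary objective reads: "To validate the TM-EMG sensor as a non-invasive technique for the assessment of neuromuscular function in the upper airway". Both endpoints concern EMG findings only.

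**The concern.** The case for the probe is that it spares the participant the pain, bleeding and infection risk of a needle in the mouth. A first study of such a device would be expected to report, at least descriptively, what the probe itself did to the people it was used on. As planned, bleeding or irritation found at a shared site at the end of the session could have come from either of two probe placements or from up to three needle insertions. Nausea, sore throat or fever reported later belongs to the whole session. Needle effects could be charged to the probe, or probe effects dismissed as needle effects.

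The loss cannot be repaired afterwards: once the needle has entered a shared site, the needle-free observation there is gone. The study is described as a pilot for a larger multi-site study, whose planners would have little on the probe's tolerability to work from.

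**Working it through.** **1. Sites and applications per participant (EMG Testing Procedure)**
- TM-EMG sites: 3 muscles × 2 sides = 6. Needle sites: 2 muscles × 2 sides = 4. Both agree with the protocol's stated totals.
- Shared sites: 4 of 6 (67%). Probe-only sites: 6 − 4 = 2 of 6 (33%), the two palatopharyngeus muscles.
- Probe placements: 4 (co-investigator) + 6 (principal investigator) = 10.
- Needle insertions: 4 × 1 = 4 up to 4 × 3 = 12.

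**2. Over the whole study (Study Summary)**
- Participants: 10 neuromuscular + 5 OSA + 8 healthy = 23.
- TM-EMG sites: 23 × 6 = 138, of which 23 × 4 = 92 are shared and 23 × 2 = 46 are probe-only.
- Probe placements: 23 × 10 = 230. Needle insertions: 23 × 4 = 92 to 23 × 12 = 276.

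**3. What each planned observation can separate**

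| Observation | Timing | Separates devices? |
|---|---|---|
| Site examination | once, after all testing | not at the 4 shared sites; possible at the 2 probe-only sites if recorded by site, which is not specified |
| Vital signs | before and after all testing | no |
| Day 1 and day 7 contacts | after the combined session | no, apart from harms specific to one device by nature (probe-tip allergy, needle-site infection) |
| Stopped muscle test | during one test | yes, if the device in use is recorded, which is not required |

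**4. What a check before the first needle would yield**

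With zero events in n participants, the exact one-sided 95% upper bound on the event rate is 1 − 0.05^(1/n). For n = 23: 1 − 0.05^(1/23) = 12.2%. The two-sided 95% interval has upper limit 1 − 0.025^(1/23) = 14.8%. Both assume that all 23 complete the co-investigator's pass, and both cover the palatoglossus and genioglossus only.

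The documents give no true event rate. Under assumed per-participant rates p, the chance of seeing at least one event in 23 is 1 − (1 − p)^23: 21% for p = 1%, 69% for p = 5% and 91% for p = 10%. The check would probably reveal common effects and could easily miss rare ones.

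**The case against.** A reader might infer that harms cannot be assigned to either device at all, or that no probe-only rate could ever be stated. The documents do not support that. Two of the six sites never receive a needle, so a local finding there cannot come from one. Some disclosed risks belong to one device by nature. Gag or pain occurs while a known device is in use, and intolerance is handled one muscle test at a time. The gap is in what is recorded; it is not an unavoidable result of the design. Testing both devices at the same place in one session is what a paired comparison of recordings needs.

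A reader might also infer that the primary objective's non-invasive claim goes untested. In the literal sense, no tissue penetration, the word describes the device and needs no test. The hypothesis and both endpoints concern diagnostic findings, and the follow-on study is meant to show diagnostic usefulness, so no stated aim fails.

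These points stand, and so do the limits on what a remedy can deliver. The co-investigator's pass omits the palatopharyngeus, where the protocol itself expects trouble with gagging. Benzocaine precedes all probe contact. The probe always precedes the needle at a shared site, and the principal investigator's second probe placement comes immediately before the needle.

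None of this restores the information at the four shared sites. Attribution there remains possible only if something is recorded before the needle, and the plan asks for nothing at that moment. The palatopharyngeus helps only if findings are logged by site. Its testing is also described after the needle work, so a general effect such as nausea could carry over if it is done in that order.

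**Conclusion.** The point holds as a gap in planned data capture. At 4 of the 6 TM-EMG sites (92 of 138 over the study), local harms are not separable by device from the data the plan collects. The same is true of general effects such as nausea or sore throat, unless the device in use at onset happens to be noted. The probe-only sites and acute intolerance offer partial attribution, but no section requires the record that would make use of it.

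Diagnostic agreement, the primary endpoint, and the OSA comparison are untouched. The loss is descriptive safety and tolerability information on the investigational device. With 23 participants this information would be modest: zero events before the needle would exclude only per-participant rates above 12.2% (one-sided 95%), assuming that everyone completes that pass. The change is worth making because it is cheap and because the observation cannot be recovered later. The conclusion rests on the published text; a case report form that already records device and site would narrow it.

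**What to change.** 1. After the co-investigator's TM-EMG pass and before the first needle insertion, inspect the four sites and record bleeding, irritation or swelling, gag or nausea, and a 0–10 discomfort score.
2. Make the same record for the probe-only palatopharyngeus sites, and after the needle at each shared site, with the number of insertions used.
3. Log every adverse event and every stopped muscle test by site and by the device in use at onset. Do not attribute by the last device applied: at the end of a shared site that is always the needle, so effects of the principal investigator's own probe placement would be charged to it.
4. Add one sentence to Statistical Methods: these data are tabulated descriptively by device and by cohort.
5. State the limits alongside the table. The pre-needle record reflects probe plus benzocaine. The probe always comes first at shared sites, so device comparisons are confounded with order. Post-needle findings at shared sites reflect both devices. Late effects (day 1 and day 7) remain attributable only to the combined session.

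Cost: one extra form and a few minutes within the 60-minute EMG visit, with no added visit, staff or invasive procedure. The downside is a slightly longer session.

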Transmembrane Electromyography (TM-EMG) for the Assessment of Neuromuscular Function in the Oropharynx

Principal Investigator: [name].

Co-Principal Investigator: [name].

Subinvestigator: [name].

Sponsor: Powell Mansfield, Inc. Funded by: Powell Mansfield, Inc.

Version 2

April 4, 2019

STUDY SUMMARY

Study Description:	Transmembrane electromyography (TM-EMG) may be a feasible and
	valid non-invasive EMG technique for detecting neuromuscular (NM)
	impairment. This study will assess whether, in healthy volunteers and
	participants with known obstructive sleep apnea (OSA) and other NM
	diseases involving the oropharynx, the same characteristic motor unit
	potentials obtained on conventional needle EMG (NEMG) can be
	obtained using a TM-EMG sensor. The purpose of this study is to
	demonstrate whether the TM-EMG sensor can provide the
	same diagnostic accuracy as the concentric needle electrode for the
	diagnosis of NM diseases. Having demonstrated diagnostic similarity of
	TM-EMG to NEMG, the secondary aim of this study is to confirm that
	NM disturbance of oropharyngeal striated muscles in participants with
	OSA can be elicited with the TM-EMG sensor.

Objectives: Primary Objective: To validate the TM-EMG sensor as a non-invasive technique for the assessment of neuromuscular function in the oropharynx.

Secondary Objective: To elicit, using the TM-EMG sensor, neuromuscular findings that correlate to OSA in affected participants.

Endpoints: Primary Endpoint: Proof of diagnostic consistency using both the TM-EMG sensor and NEMG in neuromuscular disorders affecting oropharyngeal muscles.

Secondary Endpoint: Proof that participants with known OSA exhibit EMG findings different from healthy participants and that these findings can be detected using both the NEMG and the TM-EMG sensor.

- **Study Population: I**5 total participants with disorders affecting the function of oropharyngeal muscles
 - 10 participants with one of the following neuromuscular disorders:

	 ALS with the presence of bulbar symptoms
	 muscular dystrophy with the presence of bulbar symptoms
	• 5 participants with severe OSA
	8 healthy volunteer participants
Phase:	Pilot

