related concerns. The research staff will contact the participant 1 day and 7 days after completion of the EMG test to document any adverse events the participant may have had following the testing. Responses will be documented in the EMR and serious adverse events will be reported to the study sponsor and IRB within 24 hours. Adverse events which occur more than 5 days after the EMG test will not be considered related to the study intervention, unless the investigator suspects a potential link.

Sleep Study

All healthy study participants selected for the study will be required to complete an overnight stay for an in-laboratory Polysomnogram ("PSG").

Study Endpoints

Primary Endpoint

Proof of diagnostic consistency using both the TM-EMG sensor and NEMG in neuromuscular disorders of the oropharyngeal muscles.

TM-EMG and NEMG data will be analyzed offline upon completion of testing by [name]. Analysis will include the presence of spontaneous activity (fibrillation potentials and positive sharp waves), MUP morphology (number phases, duration and amplitude) and recruitment pattern. MUP morphology will be analyzed manually. Each recording will be labeled as a normal or abnormal study. Abnormal studies will be classified into active or chronic neurogenic changes or myopathic changes.

Secondary Endpoint

Proof that participants with known OSA exhibit EMG findings different from healthy participants and that these findings can be detected using both the needle electrode and the transmembrane sensor.

Analysis results will be compared between the healthy cohort and the neurologic disorders cohort; and between the healthy cohort and the OSA cohort.

Sample Size Calculation

Given that this is a novel EMG testing technique, a formal sample size calculation was not performed. The sample size chosen for this study was based on what would be reasonably feasible given constraints in areas such as funding and recruiting. The results from this pilot study will enable design of a larger, multi-site study adequately powered to show the diagnostic usefulness of TM-EMG.

Statistical Methods

All data will be examined to determine if there are any missing or non-plausible values, and these will be removed. Summary statistics will be calculated, including means or medians, minimums and maximums, standard deviations, and interquartile ranges.

The distribution of EMG findings in OSA will be presented as descriptive statistics.

ADVERSE EVENT MONITORING

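### The primary endpoint is worded for neuromuscular disorders only, so agreement between TM-EMG and needle on normal muscle is weakly tested, although the plan already collects paired healthy and OSA recordings

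*Combined protocol and SAP*

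**What the plan says.** Under Study Endpoints, the Primary Endpoint is "Proof of diagnostic consistency using both the TM-EMG sensor and NEMG in neuromuscular disorders of the oropharyngeal muscles". The Study Summary has the same restriction, to "neuromuscular disorders affecting oropharyngeal muscles".

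The Study Population entry of the Study Summary lists "10 participants with one of the following neuromuscular disorders" (ALS or muscular dystrophy, with bulbar symptoms), then separately "5 participants with severe OSA" and "8 healthy volunteer participants".

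The Study Description is wider. It opens "This study will assess whether, in healthy volunteers and" and continues "participants with known obstructive sleep apnea (OSA) and other NM" diseases, and gives the purpose as showing diagnostic accuracy equal to that of the needle. The last paragraph of Study Background and Rationale also compares TM-EMG with needle signals across healthy, neurologic and OSA participants.

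The EMG Testing Procedure is not limited by cohort: "In total, 6 muscles locations will be tested via TM-EMG, and 4 muscle locations by NEMG". The four shared locations are the left and right palatoglossus and genioglossus. Each recording is labelled normal or abnormal, and abnormal ones are typed as active neurogenic, chronic neurogenic or myopathic. Under the Secondary Endpoint, results are compared between the healthy cohort and each disease cohort. Statistical Methods names summary statistics only: no agreement measure and no threshold.

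**The concern.** Equal diagnostic accuracy has two parts: calling diseased muscle abnormal and calling normal muscle normal. A cohort selected for bulbar symptoms can be expected to supply mostly needle-abnormal recordings and so says little about the second part. The healthy cohort supplies most of the needle-normal recordings, but as worded it is outside the primary endpoint.

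At stake is what a finding of consistency would mean. The primary objective is to validate the sensor, and the secondary aim is introduced as following once similarity to the needle has been shown. That aim contrasts OSA with healthy participants, yet the primary endpoint need not show similarity in healthy muscle at all. The pilot is also meant to inform a larger study, whose design will need an estimate of agreement on normal muscle.

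**Working it through.** The plan states no agreement target, sample-size calculation or abnormality rate, so there is no figure of its own to reproduce.

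**Pair counts** (Study Population and EMG Testing Procedure; one TM-EMG recording per shared location):
- neuromuscular: 10 × 4 = 40
- OSA: 5 × 4 = 20
- healthy: 8 × 4 = 32
- total: 92

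These are maxima, because a muscle test that a participant does not tolerate is discontinued.

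**Assumed share of needle recordings that are abnormal:** neuromuscular 60-95%, OSA 20-80%, healthy 0-10%.

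**Needle-normal pairs available to reveal over-calling** = pairs × (1 − share abnormal):
- neuromuscular: 40 × 0.05 = 2 to 40 × 0.40 = 16
- OSA: 20 × 0.20 = 4 to 20 × 0.80 = 16
- healthy: 32 × 0.90 = 28.8 to 32 × 1.00 = 32
- all three cohorts: 2 + 4 + 28.8 = 34.8 to 16 + 16 + 32 = 64

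The neuromuscular wording therefore leaves 2-16 such pairs, against about 35-64 over all cohorts.

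**A sensor that labels every recording abnormal.** Its raw agreement equals the needle-abnormal share of the pairs counted:

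| Pairs counted | Lowest assumed rates | Highest assumed rates |
|---|---|---|
| Neuromuscular (40) | 24/40 = 60% | 38/40 = 95% |
| Neuromuscular + OSA (60) | (24 + 4)/60 = 47% | (38 + 16)/60 = 90% |
| All three (92) | (24 + 4 + 0)/92 = 30% | (38 + 16 + 3.2)/92 = 62% |
| Healthy (32) | 0/32 = 0% | 3.2/32 = 10% |

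With the neuromuscular rate fixed at 90%, agreement falls from 36/40 = 90% to between (36 + 4 + 0)/92 = 43% and (36 + 16 + 3.2)/92 = 60%. Cohen's kappa for this sensor is 0 in every set that contains both needle results.

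**A sensor that over-calls only part of the time.** If it reads needle-abnormal muscle correctly but calls a fraction f of needle-normal muscle abnormal, raw agreement drops by f × (1 − share abnormal). The drop is 0.05f to 0.40f in the neuromuscular cohort and 0.90f to 1.00f in the healthy cohort. The same fault is thus between 0.90/0.40 = 2.25 and 1.00/0.05 = 20 times as visible in healthy participants.

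**A good sensor.** With 95% agreement on both needle-normal and needle-abnormal recordings, raw agreement is 95% in any mix of cohorts. Widening the endpoint does not penalise it.

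**Precision.** If all 8 healthy participants agreed, the exact 95% lower limit would be 0.025^(1/8) = 0.63, an interval of 63% to 100%.

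**The case against.** The strongest reply is that the wording is loose rather than restrictive. No analysis set is defined. The paragraph under the Primary Endpoint that describes reading and labelling has no cohort limit, and neither does the hypothesis that the two methods give similar findings. Naming neuromuscular disorders may only mark the diagnostic field. In the Study Description the word *other* also groups OSA with neuromuscular diseases, which would put up to 60 pairs in the endpoint rather than 40. This stands in part: the count of 40 is one reading, and the defect is a mismatch between statements. On either reading, healthy participants are not named in the endpoint.

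Second, the plan has checks that would partly expose an always-abnormal sensor. Such a sensor would show no TM-EMG contrast between healthy and diseased cohorts, and the secondary endpoint asks for OSA differences to be seen with both devices. Typing helps too. Suppose ALS reads neurogenic, muscular dystrophy reads myopathic, and the needle is abnormal in 90%. A sensor that always reports neurogenic then matches the type in 0.9 × 3/10 = 27% to 0.9 × 7/10 = 63% if 3 to 7 of the 10 have ALS. These safeguards are real but incomplete. The plan sets no ALS/dystrophy split, and with ten ALS participants the match would be 90%. Typing also misses a sensor that types true abnormals correctly and over-calls normal muscle. Comparing cohorts is not the same as comparing devices within healthy participants.

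Third, the illustration rests on raw agreement and assumed rates. At a 60% needle-abnormal rate the useless sensor would already look weak, and a chance-corrected statistic would show zero. This also stands, although the plan names no such statistic.

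A reader might infer that a useless sensor would pass validation. The documents do not support that: this is a descriptive pilot with no success threshold to pass.

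**Conclusion.** The point holds as a mismatch with a practical consequence. The primary endpoint is narrower than the question in the Study Description and rationale and, followed as written, leaves out of the primary result up to 32 healthy pairs and, on one reading, up to 20 OSA pairs. Over-calling of normal muscle is then weakly tested. Under the assumed rates, and on raw normal/abnormal agreement only, an always-abnormal sensor scores 60-95% in the neuromuscular cohort and about 30-62% across all cohorts.

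It does not follow that the plan discards the healthy recordings or that exactly 40 pairs form the endpoint. Healthy recordings are read and enter the between-cohort comparisons, and the wording allows OSA to be counted. What no section promises is TM-EMG/needle agreement within healthy participants or within needle-normal recordings. That gap remains whatever the true abnormality rates are; how much it matters depends on them.

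**What to change.** Before the recordings are read:

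- Define the primary endpoint as paired TM-EMG/NEMG consistency at the four shared locations in all three cohorts.
- Name the TM-EMG recording to be paired. Both the co-investigator and the principal investigator record these locations; use the principal investigator's, made at the same location as the needle.
- Report agreement separately for needle-normal and needle-abnormal recordings and by cohort, descriptively, with intervals that allow for several sites per participant. Keep the neuromuscular-only result as one of these displays.
- Limit any conclusion of diagnostic consistency to the strata in which it was shown.

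The cost is endpoint wording and a few more table rows; no new visit or recording is needed. The drawbacks are that the overall figure may be less favourable and that estimates from 8 healthy participants will be imprecise, which is a reason to report them cautiously rather than leave them out.

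### The primary endpoint and objective promise proof and validation, but the study is a feasibility-sized descriptive pilot with no agreement criterion and limited precision even if agreement is perfect

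*Combined protocol and SAP*

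**What the plan says.** The Primary Endpoint under Study Endpoints is "Proof of diagnostic consistency using both the TM-EMG sensor and NEMG in neuromuscular disorders of the oropharyngeal muscles". The Study Summary carries a near-identical version. The Primary Objective under Objectives and Hypothesis is "To validate the TM-EMG sensor as a non-invasive technique for the assessment of neuromuscular function in the upper airway". The Study Description in the Study Summary sets the aim of showing that the sensor offers the "same diagnostic accuracy as the concentric needle electrode for the" diagnosis of neuromuscular disease. It then introduces the OSA aim with the words "Having demonstrated diagnostic similarity of" TM-EMG to NEMG.

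The Study Population entry lists "10 participants with one of the following neuromuscular disorders", "5 participants with severe OSA" and "8 healthy volunteer participants", which makes 23 in all. The Sample Size Calculation section says that the size rests on feasibility, without a formal calculation, and adds: "The results from this pilot study will enable design of a larger, multi-site study adequately powered to show the diagnostic usefulness of TM-EMG". Statistical Methods provides for summary statistics only. No agreement measure, confidence interval, test, margin or threshold appears anywhere.

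The EMG Testing Procedure has four muscle sites per participant examined by both methods. The Primary Endpoint section classifies each recording, not each participant, as normal or abnormal.

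**The concern.** The two parts of the protocol do not fit together. The endpoint, objective and Study Description state a confirmatory conclusion as the outcome of this study. The Sample Size Calculation and Statistical Methods sections describe a pilot that estimates and describes, with the confirmatory step left to a successor.

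Because no criterion is attached to proof, nothing in the plan says which result would support the claim and which would not. That judgement could be made after the data are seen. A favourable count such as 10 of 10 or 9 of 10 could be presented as validation while remaining compatible with substantial disagreement between sensor and needle. It would also give the planned larger study an overconfident starting point.

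**Working it through.** The documents give no precision, power or interval, so there is no figure of theirs to reproduce. The check asks what precision perfect or near-perfect agreement would give.

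**Inputs from the documents**
- Cohorts of 10 neuromuscular, 5 OSA and 8 healthy participants (Study Summary, Study Population).
- Four sites per participant tested by both methods (EMG Testing Procedure), so at most 4 × 10 = 40 pairs in the neuromuscular cohort, counting one TM-EMG recording per site. This is a maximum, because a poorly tolerated muscle test is stopped and missing values are removed.

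**Assumptions not in the documents**
- A two-sided 95% exact (Clopper-Pearson) interval.
- A within-person correlation ρ of agreement across sites, varied from 0 to 1.

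**One result per participant.** For n agreements out of n, the lower limit is 0.025^(1/n).
- n = 10 (neuromuscular cohort): 0.025^(1/10) = 0.692, or 69%.
- n = 15 (with the OSA cohort, 10 + 5): 0.025^(1/15) = 0.782, or 78%.
- n = 23 (everyone, 10 + 5 + 8): 0.025^(1/23) = 0.852, or 85%.

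For 9 of 10, the limit is the p that solves 10p⁹(1 − p) + p¹⁰ = 0.025. This gives p = 0.555, or about 55%.

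Other interval choices for 10 of 10 change the limit only modestly:
- One-sided exact: 0.05^(1/10) = 0.741.
- Wilson: 10/(10 + 1.96²) = 0.722.

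Put the other way, a sensor whose true participant-level agreement was 80% would still show 10 of 10 with probability 0.8^10 = 0.107, about 11%.

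**One result per recording.** With 40 of 40 pairs agreeing, an approximate effective sample size is 40/(1 + 3ρ), which is then put into the same formula.

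| ρ | Effective n | Lower limit |
|---|---|---|
| 0 | 40 | 0.912 |
| 0.3 | 21.1 | 0.839 |
| 0.5 | 16 | 0.794 |
| 1 | 10 | 0.692 |

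**Size for a given precision.** With perfect participant-level agreement, the n needed for a lower limit of at least L is ln(0.025)/ln(L), rounded up.
- L = 0.80: 16.5, so 17 participants.
- L = 0.90: 35.01, so 36 participants, against 23 in the whole study.

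**The case against.** The strongest reply is that the limitation is disclosed. The protocol labels itself a pilot, admits that the size is a matter of feasibility, plans only descriptive analysis and contains no test that could declare success. This stands as far as the sample size goes: the small size is not the fault. It does not rescue the endpoint and objective, because the disclosure is exactly what their wording contradicts.

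Four stronger readings are tempting, and the documents do not support them.

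- *The primary conclusion is unreachable whatever the data show.* That would need a success criterion, and there is none. A lower limit of 69% fails a threshold of 70% but passes one of 65%. What can be shown is that proof is undefined, not that it is impossible.
- *69% is the best the design can give.* It holds for 10 participants with one result each. The plan labels recordings, and for 40 of 40 pairs 69% is the fully correlated, least favourable case.
- *The denominator is certainly 10.* The Study Population list, which applies the term neuromuscular disorders to the group of 10, favours this. But the Study Description speaks of OSA and other neuromuscular diseases together, so 15 is arguable. The Study Description also includes healthy volunteers in its comparison of the two methods, which would give 23.
- *The OSA aim is conditional on success in the primary aim.* The summary phrase suggests this, but the Secondary Endpoint section makes the comparison of the healthy and OSA cohorts without any condition.

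Nor does the plan oblige anyone to report 9 of 10 as proof. The risk is that nothing in it prevents that.

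**Conclusion.** The point holds as a mismatch between claim and design. The endpoint and objective promise proof and validation. The study is a feasibility-sized descriptive pilot with no agreement statistic, unit of analysis or criterion, and it assigns the demonstration of diagnostic usefulness to a later study.

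The size depends on the unit and the denominator, which the plan leaves open. Under a two-sided exact 95% interval, perfect agreement gives a lower limit of 69% for 10 participants with one result each and 78% for 15. For 40 paired recordings in 10 participants it lies between 69% and 91%, according to a correlation that has to be assumed. The upper end requires four sites in one person's mouth to behave as independent. One discordant participant in 10 lowers the participant-level limit to about 55%. These figures justify the word estimate; they do not show that every conceivable standard of consistency is out of reach.

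**What to change.** 1. In the Study Summary and under Study Endpoints, reword the primary endpoint to: *Estimate, with 95% confidence interval, of TM-EMG/NEMG diagnostic agreement*.
2. Name the unit and the cohort. Either define one result per participant, with a rule for combining the four sites and an exact interval, or use agreement per recording with an interval that accounts for clustering of sites within participants. State whether OSA participants count towards this endpoint.
3. Reword the primary objective, in both places, to obtaining preliminary evidence on the validity of the sensor. Bring the Study Description's aim of equal diagnostic accuracy into line, and keep proof and validation for the later powered study.
4. Add the achievable precision to Sample Size Calculation, always with its unit and assumption, for example: *participant level, n = 10, perfect agreement: two-sided exact 95% lower limit 69%*. The figure without its unit would mislead.
5. Align the summary phrase that presents similarity as already demonstrated with the unconditional OSA-healthy comparison in the Secondary Endpoint section.

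The cost is edits to the summary, objective, endpoint and sample size text, plus one interval in the analysis. No participants or procedures are added. The downside for the sponsor is a less favourable claim.
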